# 3.3.2.2.3 Disease control rate

DCR analysis is based on an estimand defined according to the following attributes:

- The endpoint is disease control response (confirmed CR or PR or SD as BOR) as per RECIST 1.1.
- The treatment condition of interest is tusamitamab ravtansine loading dose Q2W in combination with ramucirumab.
- The analysis population is the participants from all-treated population (defined in Section 2) treated at the RD of tusamitamab ravtansine loading-dose Q2W regimen (ie, excluding participants treated at the starting dose if this differs from the RD).
- Intercurrent events:
  - The study intervention discontinuation will be handled with the treatment policy strategy. Disease control response will be assessed based on tumor assessments regardless of study intervention discontinuation.
  - The further anticancer therapy (defined as all further systemic anti-cancer therapies) intercurrent event will be handled with the "while not initiating further anticancer therapy" strategy. Disease control response will be assessed based on tumor assessments done up to the initiation of further anticancer therapy.
- The population-level summary will include the disease control rate, defined as the rate of participants with disease control response and 2-sided 95% CIs using the Clopper-Pearson method.

In the absence of confirmed objective response and SD before the analysis cut-off date (taking into account the intercurrent event handling strategies), participants will be considered as non-DCR, whatever the reason (including participants with non-evaluable BOR).

Disease control rate will also be summarized on the activity population as a supplementary analysis.

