 - Duration of response will be summarized for the subgroup of participants who achieve confirmed objective response on the all-treated population with descriptive statistics using Kaplan-Meier methods. The median DOR and associated 95% CI will be provided.
 - Progression-free survival will be summarized on the all-treated population using Kaplan-Meier methods. The median PFS times and associated 95% CI will be provided, along with probabilities of being progression-free at different time points.
 - Disease control rate will be summarized on the all-treated population using descriptive statistics and 95% CIs will be provided using the Clopper-Pearson method. As a supplementary analysis, DCR will also be summarized on the activity population.
- **Analysis of safety endpoints:**
 - Number and percentage of participants experiencing TEAEs by primary system organ class (SOC) and preferred term will be summarized by NCI-CTCAE V5.0 Grade (all grades, and Grade ≥ 3) on the all-treated population. Similar summaries will be prepared for TEAEs related to IMP, TEAEs leading to permanent full/partial intervention discontinuation, TEAEs leading to dose modification or dose interruption, serious TEAEs, TEAEs with fatal outcome, adverse events of special interest (AESIs), and AEs/SAEs occurring during the posttreatment period. In addition, the number (%) of participants with any Grade 5 AE (TEAE and posttreatment) will be summarized.
 - Hematology and clinical chemistry results will be graded according to the NCI-CTCAE V5.0, when applicable. Number and percentage of participants with laboratory abnormalities (all grades and by grade) using the worst grade during the on-treatment period will be provided on the all-treated population.

Data Monitoring/Other committee: Yes

[figure not shown]
Study Committee (SC; Part 1)

The SC includes the Investigators or designees and Sponsor team members and, when appropriate, ad hoc experts. The SC will have regular meetings every 2 weeks during Part 1 (safety run-in phase) of the study.

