9.3.3.3 Disease control rate

Analysis of the DCR will be based on a treatment policy and composite variable estimand defined according to the following attributes:

- The endpoint is disease control response (confirmed CR or PR, or SD as BOR) as per RECIST 1.1.
- The treatment condition of interest is tusamitamab ravtansine loading dose Q2W in combination with ramucirumab.
- The analysis population is the subgroup of participants from all-treated population (defined in [Section 9.2](#) Population for analyses) treated at the recommended dose of tusamitamab ravtansine in a loading-dose Q2W regimen (ie, excluding participants treated at the starting dose, if this differs from the recommended dose).
- Intercurrent events:
 - The study intervention discontinuation intercurrent event will be handled with the treatment policy strategy. Disease control response will be assessed based on tumor assessments regardless of study intervention discontinuation.
 - The other anticipated intercurrent events will be handled with the composite strategy. Participants who discontinue the study, start an anticancer therapy, experience PD, or die prior to observing a disease control response will be considered nonresponders.
- The population-level summary will be the disease control rate (DCR), defined as the rate of participants with disease control response and two-sided 95% CIs using the Clopper-Pearson method. In the absence of a disease control response, participants will be considered as nonresponders, whatever the reason (including participants with missing or nonevaluable BOR).

As a supplementary analysis, DCR as per RECIST 1.1 will also be summarized on the subgroup of participants from activity population (defined in [Section 9.2](#) Population for analyses) treated at the recommended dose of tusamitamab ravtansine in a loading-dose Q2W regimen (ie, excluding participants treated at the starting dose if this differs from the recommended dose). The same analytical approach as described above will be used.

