### 3.2.2 Main analytical approach

#### 3.2.2.1 Confirmed objective response

The primary efficacy analysis is based on the primary estimand for part 2 introduced in Section 1.2.1. This primary estimand is defined according to the following attributes:

- The primary efficacy endpoint is confirmed objective response (confirmed CR or PR as BOR) as per RECIST 1.1. based on the investigator's assessment as defined in Section 3.2.1.2.
- The treatment condition of interest is tusamitamab ravtansine loading dose Q2W in combination with ramucirumab.
- The analysis population is the participants from all-treated population (defined in Section 2) treated at the RD of tusamitamab ravtansine loading dose Q2W regimen (ie, excluding participants treated at the starting dose, if this differs from the RD).
- Intercurrent events:
  - The study intervention discontinuation intercurrent event will be handled with the treatment policy strategy. Confirmed objective response will be assessed based on tumor assessments regardless of study intervention discontinuation.
  - The further anticancer therapy (including further systemic anticancer therapies) intercurrent event will be handled with the "while not initiating further anticancer therapy" strategy. Confirmed objective response will be assessed based on tumor assessments done up to the time of initiation of further anticancer therapy.

• The population-level summary will be the ORR, defined as the rate of participants with confirmed objective response and 2-sided 95% CIs using the Clopper-Pearson method.

In the absence of confirmed objective response before the analysis cut-off date (taking into account the intercurrent event handling strategies), participants will be considered as non-responders, whatever the reason (including participants with missing or non-evaluable BOR).

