# 3.2.4 Supplementary analyses

Number (%) of participants within each BOR category, including not evaluable as per RECIST 1.1 and reason for being not evaluable will be provided on the subgroup of participants from the all-treated population treated at the RD (ie, excluding participants treated at the starting dose if this differs from the RD).

As a supplementary analysis, confirmed objective response as per RECIST 1.1 will also be summarized on the subgroup of participants from activity population (defined in Section 2) treated at the RD for tusamitamab ravtansine in a loading-dose Q2W regimen (ie, excluding participants treated at the starting dose if this differs from the RD). The same analytical approach as described above will be used.

In addition, the best relative tumor change from baseline, defined as the smallest relative tumor change from baseline (where tumor change at time t is the difference between sum of the longest diameters of the target lesions at time t and baseline, resulting in a negative value in case of decrease), will be summarized using a waterfall plot on the participants on the all-treated population treated at the RD (ie, excluding participants treated at the starting dose if this differs from the RD). A swimmer plot will also be provided reporting the duration of treatment for all participants with their overall response and some baseline characteristics. This plot will differentiate responders from non-responders. In addition, a spider plot will also be provided reporting the tumor change from baseline over the time.

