#### 3.7.1.3.2 Circulating CEA levels at baseline and clinical response

Circulating CEA levels before IMP administration will be correlated with confirmed objective response (for all treated participants). To this end, the last circulating CEA assessment before (closest to) IMP administration will be considered and reported as the baseline value.

Baseline circulating CEA values will be presented using descriptive statistics by response status and overall. The confirmed objective response rate and two-sided 95% CIs using the Clopper-Pearson method will be presented for each circulating CEA subgroups (base on the predefined thresholds).

The correlation between the circulating CEA levels (quantitative) and the tumor burden at baseline will be also assessed and visualized graphically. To this end, Pearson correlation, Spearman's rank, or Kendall's tau coefficient will be considered depending on the nature of the data.

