# 3.7.1.3.4 Mutational profiling

Genomic alterations locally assessed and entered in the eCRF at prescreening as per protocol will be presented. For each gene, participants will be grouped into two groups: "altered" (ie, participants with at least one alteration for the gene) and "wild-type" (ie, participants without alteration for the gene) and described using descriptive statistics by IHC CEACAM5 expression and overall. The confirmed objective response rate and two-sided 95% CIs using the Clopper-Pearson method will be presented for each gene in the all-treated population.

Circulating-free DNA (cfDNA) centrally assessed may be also generated and will be analyzed in the same way as genomic alterations entered locally in the eCRF.

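### The SAP's supplementary DCR leaves out the recommended-dose limit that protocol section 9.3.3.3 sets, so it would pool two loading doses if DL -1 is selected

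*SAP*

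**What the plan says.** SAP section 3.3.2.2.3 defines the main DCR on all-treated participants who received the recommended dose (RD). Its last sentence adds a further analysis: "Disease control rate will also be summarized on the activity population as a supplementary analysis". That sentence carries no dose condition. SAP Table 4 defines the activity population by measurable disease and post-baseline evaluability (or early clinical progression or death from the disease), also without reference to dose.

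Protocol section 9.3.3.3 describes the same analysis more narrowly: "As a supplementary analysis, DCR as per RECIST 1.1 will also be summarized on the subgroup of participants from activity population", and it continues by requiring treatment at the RD. The section words the exclusion for its main DCR population as "loading-dose Q2W regimen (ie, excluding participants treated at the starting dose, if this differs from the recommended dose", and the supplementary sentence repeats it in nearly identical terms.

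The SAP keeps the limit for the parallel response analysis. In section 3.2.4 the supplementary ORR "will also be summarized on the subgroup of participants from activity population (defined in Section 2) treated at the RD". The primary ORR in SAP section 3.2.2.1 is likewise defined by "excluding participants treated at the starting dose, if this differs from the RD".

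**The concern.** Two companion supplementary analyses, ORR and DCR on the activity population, are meant to be read side by side, and the protocol gives both the same RD limit. The SAP repeats the limit for ORR and not for DCR. Taken literally, the DCR sentence brings in participants treated at a starting dose that was not carried forward.

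What is at stake is modest and conditional. If DL -1 becomes the RD, the supplementary DCR would describe a mixture of two loading doses, its denominator would differ from that of the supplementary ORR, and it would not be the analysis the protocol specifies. No hypothesis is tested, so no error rate is involved.

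**Working it through.** **1. The plan's own counts.** Prescreening failure is 70% and screening failure 20% (protocol 9.1, SAP 4). Then 158 × 0.30 × 0.80 = 37.92, which reproduces the planned 38 treated. Part 2 adds 26 participants to 6 from Part 1, and 26 + 6 = 32 evaluable for activity at the RD. Both figures reproduce.

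**2. Texts side by side.**

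| Output | Protocol | SAP |
|---|---|---|
| Main DCR | All-treated, RD only (9.3.3.3) | All-treated, RD only (3.3.2.2.3) |
| Supplementary ORR | Activity, RD only (9.3.2.2) | Activity, RD only (3.2.4) |
| Supplementary DCR | Activity, RD only (9.3.3.3) | Activity, no dose limit stated (3.3.2.2.3) |

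Only the last row disagrees. No general SAP rule supplies the missing limit: the by-dose-level rule in section 3.6 covers safety, and section 3.7.1.1 has its own for PK concentrations.

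**3. When it matters.** If the starting dose is the RD, the exclusion removes nobody and both wordings give the same output. If DL -1 is the RD, the two wordings differ by the k activity-population participants who received the starting dose.

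**4. Size.** Let x of 32 have disease control at the RD, and y of k at the other dose.

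- RD-only rate = x/32; pooled rate = (x + y)/(32 + k).
- Pooled minus RD-only = [k/(32 + k)] × (y/k − x/32).
- 95% Clopper-Pearson limits for r of n: lower = Beta⁻¹(0.025; r, n − r + 1), upper = Beta⁻¹(0.975; r + 1, n − r).

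The documents give no value for k. I assume k = 6, which is 38 − 32. The other dose then has weight 6/38 = 15.8%. The counts x are also assumed.

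| x at RD | RD only | Pooled, y = 0 | Pooled, y = 3 | Pooled, y = 6 |
|---|---|---|---|---|
| 16 | 16/32 = 50.0% (31.9 to 68.1) | 16/38 = 42.1% (26.3 to 59.2) | 19/38 = 50.0% (33.4 to 66.6) | 22/38 = 57.9% (40.8 to 73.7) |
| 20 | 20/32 = 62.5% (43.7 to 78.9) | 20/38 = 52.6% (35.8 to 69.0) | 23/38 = 60.5% (43.4 to 76.0) | 26/38 = 68.4% (51.3 to 82.5) |
| 24 | 24/32 = 75.0% (56.6 to 88.5) | 24/38 = 63.2% (46.0 to 78.2) | 27/38 = 71.1% (54.1 to 84.6) | 30/38 = 78.9% (62.7 to 90.4) |

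For x = 20 the shift runs from 0.158 × (0 − 0.625) = −9.9 percentage points to 0.158 × (1 − 0.625) = +5.9 points.

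The width of the range depends on k. With x = 20 and k = 3 it is 20/35 = 57.1% to 23/35 = 65.7%; with k = 9 it is 20/41 = 48.8% to 29/41 = 70.7%.

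**The case against.** The strongest reply is that the limit is implied. The sentence closes a section whose estimand is already restricted to the RD, the SAP is based on the protocol, and the protocol states the full rule for this output. The documents also use shorthand elsewhere. The protocol synopsis says only "As a supplementary analysis, DCR will also be summarized on the activity population", and it shortens the ORR in the same way. A careful programmer could reasonably add the limit, so it would go too far to say there is no textual basis for it. What remains is that the SAP sentence names a new population with no dose limit, while the parallel ORR sentence in section 3.2.4, in the same position after a restricted main analysis, writes the limit out. The two readings give different tables, and the SAP should settle which applies.

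Several stronger readings are tempting, and the documents do not support them:

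- **ORR by circulating CEA and by gene.** A reader might infer that the SAP dropped a protocol limit here too. SAP 3.7.1.3.2 says "Circulating CEA levels before IMP administration will be correlated with confirmed objective response (for all treated participants", and SAP 3.7.1.3.4 says the rates "will be presented for each gene in the all-treated population". But protocol section 9.3.4 leaves the CEA analyses to the SAP, and the protocol sets no population for ORR by gene. The SAP names all treated participants explicitly, which is a defensible exploratory choice, especially as both dose levels share the same regimen from Cycle 2.
- **The DCR sentence as the only exception.** The swimmer and spider plots in SAP 3.2.4 and the subgroup analyses in 3.7.2 state no RD limit either. The point rests on the contradiction with the protocol for this output.
- **The version history.** It does not list this difference, but it is headed as a record of major changes, so its silence shows little about intent.
- **Six as an upper bound.** It is the difference between 38 treated and 32 activity-evaluable participants, which are different kinds of count. DLT-nonevaluable participants are replaced, and the decision tree is not shown in the supplied text.

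**Conclusion.** The point holds for the supplementary DCR only. SAP section 3.3.2.2.3 as written conflicts with protocol section 9.3.3.3 and is out of step with the supplementary ORR in SAP section 3.2.4. The effect is nil if the starting dose is confirmed, and the documents do not say which dose was. If DL -1 is selected, the illustration moves a DCR of 62.5% to somewhere between 52.6% and 68.4%, with widely overlapping intervals. That range assumes 32 participants at the RD, 20 of them with disease control, and 6 starting-dose participants who all belong to the activity population. This is a minor inconsistency in a supplementary output; no main efficacy analysis depends on it.

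**What to change.** In the last sentence of SAP section 3.3.2.2.3, limit the activity population to participants treated at the RD, with the qualifier already used in section 3.2.2.1: "excluding participants treated at the starting dose, if this differs from the RD". The cost is one phrase. It needs no new data and no protocol change, and the filter is the one the supplementary ORR already requires. If pooling is in fact intended, the SAP should record the departure from protocol section 9.3.3.3 and show the result by dose level. No change is required to SAP sections 3.7.1.3.2 or 3.7.1.3.4.

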# 3.4 TERTIARY/EXPLORATORY ENDPOINT(S) ANALYSIS

Analyses of tertiary/exploratory endpoints (eg, biomarkers) are defined in Section 3.7.1.3.

# 3.5 MULTIPLICITY ISSUES

No multiplicity issues are handled in this study.

# 3.6 OTHER SAFETY ANALYSES

All safety analyses will be performed on the all-treated population as defined in Section 2, by dose level (if applicable) and overall, unless otherwise specified, using the following common rules:

- The analysis of the safety variables will be essentially descriptive, and no testing is planned.
- Safety data in participants who do not belong to the all-treated population (eg, treated but not enrolled) will be provided.

# 3.6.1 Extent of exposure

#### 3.6.1.1 Overall exposure

The dose information will be assessed by the following variables:

- Overall number of cycles started, defined by the number of cycles in which at least one dose of any study interventions is administered.
- Duration of overall exposure (in weeks) is defined as (Last day of exposure first day of exposure +1)/7.
  - The first day of exposure is defined as the first administration date with non-zero dose for at least one of the IMP (tusamitamab ravtansine or ramucirumab).
  - The last day of exposure is the day before the theoretical date of the next administration (after the last administration), defined as the last administration date of at least one IMP + 14 days 1 (tusamitamab ravtansine and ramucirumab).

The total number of cycles started, and the number of cycles started by participants will be summarized as a quantitative variable and by category (number (%) of participants receiving at least 1 cycle, at least 2 cycles, etc). The duration of overall exposure will be summarized quantitatively.

The following variable will be computed to describe overall dose modification (cycle delay):

• Cycle delay: A cycle is deemed as delayed if the start date of the current cycle – 14 days – start date of the previous cycle is >2 days. Cycle delay is not defined for the first cycle.

Cycle delay will be analyzed at the participant (with number of participants used as denominator) and cycle (with number of cycles used as denominator) levels, as follows:

- Number (%) of participants with a least 1 cycle delayed
  - Number (%) of participants with a cycle delayed between 3 and 7 days (using maximum delay across all cycles)
  - Number (%) of participants with a cycle delayed between 8 and 14 days (using maximum delay across all cycles)
  - Number (%) of participants with a cycle delayed >14 days (using maximum delay across all cycles)
- Number (%) of cycles delayed
  - Number (%) of cycles delayed between 3 and 7 days
  - Number (%) of cycles delayed between 8 and 14 days
  - Number (%) of cycles delayed >14 days

#### 3.6.1.2 Tusamitamab ravtansine exposure

The dose information will be assessed by the following:

- Total number of cycles started
- Number of cycles started per participant.
- Duration of tusamitamab ravtansine exposure (in weeks) is defined by date of last administration of tusamitamab ravtansine + number of theoretical days until the next administration date of first administration of tusamitamab ravtansine/7.
- Actual dose (in mg/m^2). In case of dose interruption, actual dose will be the sum of the actual doses administered before and after the dose interruption.
- Cumulative dose (mg/m^2): the cumulative dose is the sum of all actual doses of tusamitamab ravtansine, given from first to last administration.
- Actual dose intensity (ADI in mg/m^2/week): defined as the cumulative dose divided by the duration of tusamitamab ravtansine exposure (in weeks).

- 17-Jul-2023 Version number: 1
- Planned dose intensity (PDI in mg/m^2/week): corresponds to the planned dose at C1D1 + planned dose at subsequent cycles multiplied by the theoretical total number of doses started and divided by the theoretical cycle duration expressed in weeks (ie, 2 weeks per cycle started). Note: Theoretical total number of doses started is derived based on cycles where at least one IMP is administered (even in case of dose omission), up to the end of treatment of tusamitamab ravtansine.
- Relative dose intensity (RDI, in %):  $100 \times \frac{\text{ADI}(\text{mg/m}^2/\text{week})}{\text{PDI}(\text{mg/m}^2/\text{week})}$ .

The total number of cycles started and the number of cycles started by participant will be summarized as a quantitative variable and by category (number [%] of participants receiving at least 1 cycle, at least 2 cycles, etc). Duration of tusamitamab ravtansine exposure, cumulative dose, ADI and RDI will be summarized quantitatively.

The following variables will be derived to describe dose modifications and dose interruptions:

• Dose reduction: The first administration (loading dose) and second administration (first 100 mg/m^2 infusion) will not be counted as a dose reduction. For the third and subsequent tusamitamab ravtansine administrations, dose reduction will be determined using the dose level intervals provided in Table 5, by comparing the current dose level to the previous dose level. If the current dose level is below the dose level interval of the previous dose administration, then the current dose level is considered reduced.

Actual dose level	Dose level interval
Starting dose (100 mg/m  )	>90 mg/m²
Dose level -1 (80 mg/m  )	>72.5 mg/m² and ≤90 mg/m²
Low dose	>0 mg/m² and ≤72.5 mg/m²

Table 5 - Tusamitamab ravtansine dose reduction criteria

- Dose delay: A dose will be considered as delayed if the tusamitamab ravtansine administration date of the current cycle 14 days tusamitamab ravtansine administration date of the previous cycle is >2 days. Dose delay is not defined for the first cycle.
- Dose omission is defined as a dose not administered at the scheduled visit but administered afterwards.
- Dose interruption: A dose will be considered as interrupted if the tusamitamab ravtansine administration is stopped during an infusion regardless of whether it is restarted or not.

Dose modifications and dose interruptions will be analyzed by participant and cycle as follows:

- **Participant** (number of participants treated will be used as denominator)
  - Number (%) of participants with at least 1 dose modification
    - Number (%) of participants with at least 1 dose delayed
    - Number (%) of participants with at least 1 dose reduction
    - Number (%) of participants with at least 1 dose omission
  - Number (%) of participants with a least 1 dose interruption

- Cycle (number of cycles started will be used as denominator)
  - Number (%) of cycles with at least 1 dose modification
    - Number (%) of cycles with at least 1 cycle delayed
    - Number (%) of cycles with at least 1 dose reduction
    - Number (%) of cycles with at least 1 dose omission
  - Number (%) of cycles with at least 1 dose interruption

